8.3. Serious Adverse Events

8.3.1. Definitions

An SAE is defined as an event that meets at least 1 of the following criteria:

- Is fatal or life-threatening.
- Requires inpatient hospitalization or prolongation of existing hospitalization, unless hospitalization is a result of:
 - A routine treatment or monitoring of the studied indication not associated with any deterioration in condition.
 - An elective surgery or preplanned treatment for a pre-existing condition that is unrelated to the indication under study and has not worsened since signing the ICF.
 - A treatment on an emergency outpatient basis for an event not fulfilling any of the definitions of a SAE and not resulting in hospital admission.
 - Any social reasons and respite care, in the absence of any deterioration in the subject's general condition.
- Results in persistent or significant disability, incapacity, or a substantial disruption of a person's ability to conduct normal life functions.
- Constitutes a congenital anomaly or birth defect.
- Is considered to be an important medical event or a medically significant event that may not result in death, be immediately life-threatening, or require hospitalization but may be considered serious when, based on appropriate medical judgment, the event may jeopardize the subject or may require medical or surgical intervention to prevent 1 of the outcomes listed above.

8.3.2. Reporting

Every SAE, regardless of suspected causality (eg, relationship to study drug(s) or study procedure or disease progression), occurring after the subject has signed the ICF through the last study visit (or 60 days after the last dose of study treatment, or until the subject receives a new anticancer therapy whichever occurs earlier) must be reported to the sponsor (or designee) within **24 hours** of learning of its occurrence, unless otherwise specified by the Protocol. Any SAEs occurring more than 60 days after the last dose of study treatment should be reported to the sponsor or its designee only if the investigator suspects a causal relationship to the study drug.

Information about all SAEs is collected and recorded on the Adverse Event form of the eCRF. The investigator must assess and record the causal relationship of each SAE to each specific study treatment. The investigator must also complete the Incyte Serious Adverse Event Report Form, in English, and send the completed and signed form to the sponsor or designee within 24 hours of becoming aware of the SAE. The investigator must provide a causality assessment, that is, assess whether there is at least a reasonable possibility that the SAE is related to the specific study treatment: suspected (yes) or not suspected (no). Refer to the Incyte Reference Guide for Completing the Serious Adverse Event Report Form.

The contact information of the sponsor's study-specific representatives is listed in the investigator manual provided to each site. The original copy of the SAE Report Form and the confirmation sheet must be kept at the study site.

Investigational site personnel must report any new information regarding the SAE within 24 hours of becoming aware of the information in the same manner that the initial SAE Report Form was sent. Follow-up information is recorded on an amended or new SAE Report Form, with an indication that it is follow-up to the previously reported SAE and the date of the original report. The follow-up report should include information that was not provided on the previous SAE Report Form, such as the outcome of the event (eg, resolved or ongoing), treatment provided, action taken with study drug because of the SAE (eg, dose interrupted or discontinued), or subject disposition (eg, continued or withdrew from study participation). Each recurrence, complication, or progression of the original event should be reported as follow-up to that event.

If the SAE is not documented in the IB for the study drug (new occurrence) and is thought to be related to the sponsor's study drug, the sponsor or its designee may urgently require further information from the investigator for reporting to health authorities. The sponsor or its designee may need to issue an Investigator Notification to inform all investigators involved in any study with the same drug that this SAE has been reported. Suspected Unexpected Serious Adverse Reactions will be collected and reported to the competent authorities and relevant ethics committees in accordance with Directive 2001/20/EC, or as per national regulatory requirements in participating countries.

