Note: QTc prolongation due to pacemaker may enroll if the JTc is normal or with medical monitor approval.
14. Evidence of HBV or HCV infection or risk of reactivation. Subjects positive for HBV DNA, HCV RNA, HBsAg, or anti-HBc antibody may be included on a case by case basis with approval from medical monitor.
Note: Subjects with no prior history of hepatitis B infection who have been vaccinated against hepatitis B and who have a positive antibody against HBsAg test as the only evidence of prior exposure may participate in the study.
15. Known history of drug-induced liver injury; alcoholic liver disease; nonalcoholic steatohepatitis; primary biliary cirrhosis; or ongoing extrahepatic obstruction caused by stones, cirrhosis of the liver, or portal hypertension.
16. Known history of HIV; HIV 1/2 antibodies.
17. Known allergy or reaction to any component of nivolumab, ipilimumab, or study drug or formulation components.
18. Inability or unlikeliness to comply with the dose schedule and study evaluations, in the opinion of the investigator.
19. Women who are pregnant or breastfeeding.
20. Any condition that would, in the investigator's judgment, interfere with full participation in the study, including administration of study drug and attending required study visits; pose a significant risk to the subject; or interfere with interpretation of study data.

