5.2. Study Drugs

5.2.1. INCAGN01876

5.2.1.1. Description and Administration

The study drug (INCAGN01876) is supplied as a sterile, single-use solution for injection, in a 10 mL glass vial. Each vial contains 50 mg of INCAGN01876 in 5 mL at a concentration of 10 mg/mL in [REDACTED], and pH [REDACTED]. The infusion site should not be used for blood sampling.

Study drug will be diluted in [REDACTED] or acceptable admixture as outlined in the Pharmacy Manual and will be administered by qualified site personnel as an IV infusion over a 30-minute (-5/+10 minutes) period on Day 1 of each cycle when INCAGN01876 is scheduled to be given. On days when INCAGN01876 will be administered along with other agents administered by infusion, INCAGN01876 will be administered first, followed by a 30-minute wait before administration of the subsequent immune therapy/therapies.

In Phase 1, subjects will be administered study drug, according to cohort enrollment (see [Table 2](#)), Q2W (14-day cycles), in combination with immune therapies. In Phase 2, subjects will be administered study drug at the recommended dose Q2W (14-day cycles), in combination with immune therapies. In Treatment Group B, INCAGN01876 is only administered on Day 1 of Cycles 1 and 2.

Subjects will continue to receive INCAGN01876 as long as they are deriving benefit and have not met any of the Protocol-defined conditions for treatment withdrawal (see Section [5.5](#)), or for up to 24 months from the first dose of study treatment, whichever occurs first.

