5.4. Treatment Interruptions and Adjustments

5.4.1. Dose Modifications

Selections to the study drug (INCAGN01876) are planned for dose-escalation cohorts (see Section 4.1.1). Dose interruptions of study drug may also occur for individual study subjects. The identification of DLTs will define the doses used in planned cohorts (see Section 5.4.2). Further, the occurrence of DLTs and other toxicities (related or unrelated to study drug) will guide decisions for treatment interruptions and discontinuation for individual subjects. Intrasubject dose escalation will not be permitted.

No dose reductions of INCAGN01876 are allowed for the management of toxicities of individual subjects. Doses of INCAGN01876 may be delayed for toxicity management (see Section 5.4.6).

In the event of any significant treatment related adverse events, holding of the therapy or discontinuation as per Table 7 would be advised.

No dose reductions of nivolumab or ipilimumab are allowed for the management of toxicities of individual subjects. Doses of nivolumab and ipilimumab may be delayed for toxicity management (see Section 5.4.6). Nivolumab and ipilimumab are approved therapies and have specific subject safety management guidelines within their package insert; the treating investigator should refer to and follow the labeled guidance for both nivolumab and ipilimumab.

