5.4.7. Management of Immune-Related Adverse Events

INCAGN01876, nivolumab, and ipilimumab are considered immune modulators, and it is possible that irAEs (both nonserious and serious) may occur. Adverse events of a potential immunologic etiology or irAEs may be defined as an AE consistent with an immune phenomenon associated with drug exposure *after all other etiologies have been eliminated*. Immune-related AEs may be expected based on the nature of the study treatment, their mechanism of action, and reported experience with these and other immunotherapies. Special attention should be paid to AEs that may be suggestive of potential irAEs. An irAE can occur shortly after the first dose or several months after the last dose of treatment. Suspected irAEs should be discussed with the medical monitor when possible.

Subjects should receive appropriate supportive care measures as deemed necessary by the treating investigator. Suggested supportive care measures for the management of drug-related AEs with potential immunologic etiology are outlined in [Table 8](#). Detailed supportive care guidelines for specific irAEs can be found in [Appendix B](#). Nivolumab and ipilimumab are approved therapies and have specific irAE management guidelines within their package insert; the treating investigator may use labeled guidance or institutional guidelines for the management of irAEs if preferred. For each AE, attempts should be made to rule out other causes, including but not limited to metastatic disease or bacterial or viral infection, which might require specific supportive care.

Table 8: Supportive Care Guidelines for Immune-Related Adverse Events

CTCAE Grade/Severity	Supportive Care ^a
Grade 1 (mild)	
 • Monitor symptoms and provide symptomatic treatment.
Grade 2 (moderate)	
 • Monitor symptoms and provide symptomatic treatment. • Consider consultation with specialists as necessary. • Consider systemic corticosteroids per institutional standard of care.

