The occurrence of AEs should be sought by nondirective questioning of the subject during the screening process after signing the ICF and at each visit during the study. Adverse events may also be detected when they are volunteered by the subject during the screening process or between visits, or through physical examination, laboratory test, or other assessments. To the extent possible, each AE should be evaluated to determine:

- The severity grade (CTCAE Grade 1 to 5).
- Whether there is at least a reasonable possibility that the AE is related to the study treatment: suspected (yes) or not suspected (no).
 - **Note: causality assessment for each agent administered per study must be indicated.**
- The start and end dates, unless unresolved at final follow-up.
- The action taken with regard to study drug.
- The event outcome (eg, not recovered/not resolved, recovered/resolved, recovering/resolving, recovered/resolved with sequelae, fatal, unknown).
- The seriousness, as per SAE definition provided in Section 8.3.1.

Unlike routine safety assessments, SAEs are monitored continuously and have special reporting requirements (see Section 8.3.2).

All AEs should be treated appropriately. If an AE is treated with a concomitant medication or nondrug therapy, this action should be recorded on Adverse Event form and the treatment should be specified on the Prior/Concomitant Medications or Procedures and Non-Drug Therapy form in the eCRF.

Once an AE is detected, it should be followed until it has resolved or until it is judged to be permanent; assessment should be made at each visit (or more frequently if necessary) of any changes in severity, the suspected relationship to the study drug, the interventions required to treat the event, and the outcome.

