9. STATISTICS

9.1. Study Populations

The full analysis set includes all subjects enrolled in the study who received at least 1 dose of study drug (INCAGN01876). This population will be used in the analyses of demographic, baseline, safety, study drug administration, and efficacy data.

[REDACTED]

[REDACTED]

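### Protocol 8.3.2 ties late SAE reporting to the study drug, so read literally an SAE attributed solely to nivolumab or ipilimumab more than 60 days after the last dose need not be reported

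*Protocol*

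**What the plan says.** Protocol Section 8.3.2 has two tiers. Up to the last study visit, 60 days after the last dose or the start of new anticancer therapy, whichever is earliest, every SAE goes to the sponsor whatever its cause. The second tier covers "Any SAEs occurring more than 60 days after the last dose of study treatment". These "should be reported to the sponsor or its designee only if the investigator suspects a causal relationship to the study drug". The clock therefore runs from the last dose of study treatment, while the causality condition names the study drug in the singular.

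The protocol ties that term to INCAGN01876 in several places. Section 5.2.1.1: "The study drug (INCAGN01876) is supplied as a sterile, single-use solution for injection". Section 5.4.1: "Selections to the study drug (INCAGN01876) are planned for dose-escalation cohorts". Section 9.1 makes the same equation when it defines the full analysis set. Exclusion criterion 17 in Section 3.2 separates the agents: "Known allergy or reaction to any component of nivolumab, ipilimumab, or study drug or formulation components". Section 5.5.1 uses study treatments for all three.

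Causality is collected agent by agent. Section 8.1.2 notes that "causality assessment for each agent administered per study must be indicated", and Section 8.3.2 repeats the requirement for each SAE. On timing, Section 5.4.7, which treats all three agents as immune modulators, states: "An irAE can occur shortly after the first dose or several months after the last dose of treatment".

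**The concern.** An investigator who judges a late serious colitis to be related to ipilimumab and not to INCAGN01876 has completed the per-agent assessment correctly. On the literal wording, that investigator is then told that no report is needed.

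Three things are at stake.

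- **Combination safety.** The Phase 1 primary objective in the Synopsis concerns INCAGN01876 given with immune therapies. A late event blamed on a partner agent may still be an effect of the combination, and the sponsor cannot judge that without the report.
- **Unequal ascertainment.** The definition of a treatment-emergent AE has no upper time limit (Protocol 9.4.2.1, SAP 8.2.1), and SAP 8.2.5 plans separate tables of related SAEs for each agent. Late SAEs attributed to INCAGN01876 can enter those tables, while late SAEs attributed only to a partner need not.
- **Little else would catch these events.** Sections 6.4.1 and 8.1.2 require monitoring for new AEs for at least 60 days or until new anticancer therapy. Since Amendment 5, the last safety follow-up is also the last study visit (6.4.2, 6.4.3).

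**Working it through.** The plan states no figure for this point, so the check is mainly one of wording.

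**Step 1: what the term means.**

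- *Narrow use (INCAGN01876 only):* 5.2.1.1, 5.4.1 and 9.1 equate the two. Exclusion criterion 17 lists study drug beside the two partner agents as a separate item.
- *Looser use:* nivolumab and ipilimumab both sit under heading 5.2, Study Drugs. Section 8.1.1, and the opening sentence of 8.3.2 itself, use the form with an optional plural. Section 8.1.2 asks for causality by agent and then calls the same assessment the relationship to the study drug. Protocol 9.4.2.1 defines treatment-related AEs through study drug, and SAP 8.2.1 states the corresponding rule as relationship to any of the three agents.

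Neither use is consistent throughout, and 8.3.2 does not say which applies.

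**Step 2: where the two readings differ.** For an SAE more than 60 days after the last dose of study treatment:

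| Suspected cause | Narrow reading | Broad reading |
|---|---|---|
| INCAGN01876, with or without a partner | Report | Report |
| Nivolumab and/or ipilimumab only | No duty to report | Report |
| None of the three | No duty to report | No duty to report |

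Only the middle row is affected.

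**Step 3: where sole attribution to a partner is most plausible.** Inputs: 14-day cycles; in Group B, INCAGN01876 only on Day 1 of Cycles 1 and 2 (5.2.1.1); nivolumab from Cycle 3 Day 1 for up to 24 months from the first dose (5.2.2.1). I assume on-schedule dosing.

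- Last INCAGN01876 dose: Cycle 2 Day 1 = Day 15. First nivolumab dose: Cycle 3 Day 1 = Day 29.
- One nivolumab dose only: the 60-day limit falls on Day 29 + 60 = Day 89, which is 89 − 15 = 74 days after the last INCAGN01876 dose.
- Nivolumab for the full 24 months (about 730 days after Day 1, so Day 731): the limit falls on Day 731 + 60 = Day 791, which is 791 − 15 = 776 days after the last INCAGN01876 dose. At 30.4 days per month that is about 25.5 months.

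In the other groups of the current protocol, INCAGN01876 continues alongside its partners, and 5.4.6 and 5.5.1 have all treatments discontinued together. The corresponding gap there is generally about 60 days.

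**Step 4: how large Group B can be.** Protocol 9.2.1 allows up to 9 subjects at each of 6 dose levels: 9 × 6 = 54 evaluable subjects. With the four levels in SAP Table 1, it is 9 × 4 = 36.

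**The case against.** The best counter-argument is that the sponsor meant all three agents. The SAP reads similar causality wording that way. Where the reporting sections clearly mean INCAGN01876 alone, as in the later part of 8.3.2 and in 8.5, they speak of the sponsor's study drug, a qualifier missing from the late-SAE sentence. This stands as evidence of intent, and it rules out the claim that the protocol reserves the term for INCAGN01876 alone. It does not settle the sentence: sites work from the protocol, whose explicit equations of the term point the other way. If the broad reading was intended, the correction is uncontroversial.

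The effect is also limited. INCAGN01876 is an immune modulator, so an investigator may often be unable to exclude it, and any suspicion makes the event reportable. Toxicities related to treatment that began earlier are followed under 5.5.2. Section 6.4.1 stops AE and SAE collection once new anticancer therapy starts, whichever agent is suspected. Enrollment is complete according to the Amendment 5 rationale. All of this stands and keeps the point small. Subjects were nevertheless still on treatment or in follow-up at that amendment, and the sentence governs their late SAEs.

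It might also be said that the partner drugs are marketed and their manufacturers would hear of such events. The documents describe no such route for SAEs; Section 8.8 sends only certain product complaints to the manufacturer.

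**Conclusion.** The concern holds as an ambiguity in a safety-reporting rule. On its literal reading, the rule leaves out SAEs that arise more than 60 days after the last dose of any study treatment and are attributed solely to nivolumab or ipilimumab. This conclusion rests on the protocol's own equations of study drug with INCAGN01876; on the looser usage found elsewhere there is no gap, only unclear wording.

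Three stronger readings are tempting, and the documents do not support them:

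- That late immune-related events are lost in general. Those with any suspected link to INCAGN01876 stay reportable.
- That the limit is study Day 60. It is 60 days after the last dose of study treatment.
- That a number of lost SAEs can be given. The documents contain no rate of late SAEs attributed solely to a partner, and multiplying a guessed rate by the planned 384 to 1039 subjects would not supply one. Group B, the clearest case, has at most 54 evaluable subjects and cannot stand for the whole trial.

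**What to change.** In the late-SAE sentence of Protocol 8.3.2, replace the study drug with any study treatment (INCAGN01876, nivolumab, or ipilimumab), and carry the same wording into the SAE completion guidance. This matches the per-agent causality already required in 8.1.2 and 8.3.2 and the reading in SAP 8.2.1. It changes what is reported to the sponsor and leaves clinical management untouched. The cost is one phrase and a few additional SAE reports.

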8.4. Emergency Unblinding of Treatment Assignment

Not applicable.

8.5. Pregnancy

Pregnancy, in and of itself, is not regarded as an AE unless there is suspicion that study drug may have interfered with the effectiveness of a contraceptive medication or method. When a pregnancy has been confirmed in a subject during maternal or paternal exposure to study drug, the following procedures should be followed in order to ensure subject safety:

- The study treatment must be discontinued immediately (female subjects only).
- The investigator must complete and submit the Incyte Clinical Trial Pregnancy form to the sponsor or its designee within **24 hours** of learning of the pregnancy.
- A serum pregnancy test must be performed to confirm the urine pregnancy test result. If a negative serum test does not confirm the urine pregnancy result, then:
 - The investigator will use his or her expert judgment, based on an assessment of the potential benefit/risk to the subject, to determine whether it is in the subject's best interest to resume study treatment and continue participation in the study.
- The EOT visit evaluations must be performed.

Data on fetal outcome and breastfeeding are collected for regulatory reporting and drug safety evaluation. Follow-up should be conducted for each pregnancy to determine outcome, including spontaneous or voluntary termination, details of the birth, and the presence or absence of any birth defects, congenital abnormalities, or maternal and/or newborn complications, by following until the first well-baby visit. Pregnancy should be recorded on a Clinical Trial Pregnancy form and reported by the investigator to the sponsor or its designee. Pregnancy follow-up information should be recorded on the same form and should include an assessment of the possible causal relationship to the sponsor's study drug to any pregnancy outcome, as well as follow-up to the first well-baby visit or the duration specified in local regulations, whichever is later. Refer to the Incyte Reference Guide for Completing the Clinical Trial Pregnancy Form.

Any SAE occurring during pregnancy must be recorded on the SAE report form and submitted to the sponsor or designee.

8.6. Warnings and Precautions

Special warnings or precautions for the study drug, derived from safety information collected by the sponsor or its designee, are presented in the Investigator's Brochure. Additional safety information collected between IB updates will be communicated in the form of Investigator Notifications. Any important new safety information should be discussed with the subject during the study, as necessary. If new significant risks are identified, they will be added to the ICF.

